4.4.2 Primary, subgroup and sensitivity analyses

Primary analysis

1. Association between adverse child outcomes and macrolide (versus penicillins) prescription during pregnancy (from 5 GW to delivery).
2. Association between adverse child outcomes and macrolide (versus penicillins) prescription during 1st trimester (from 5 to 13 GW).
3. Association between adverse child outcomes and macrolide (versus penicillins) prescription during 2st to 3rd trimester (from 14 GW to delivery).

Subgroup analyses

1. Association between adverse child outcomes and macrolide (versus penicillins) prescription during pregnancy, by macrolide subtype (erythromycin, clarithromycin and azithromycin).

2. Association between adverse child outcomes and macrolide (versus penicillins) prescription during pregnancy, by duration of antibiotics prescription (<7days and >=7days).

Sensitivity analyses

1. To evaluate the effect of potential confounding due to maternal baseline characteristics: association between adverse child outcomes and macrolide (versus penicillins) prescription 10-50 weeks prior to pregnancy (negative control analysis).
2. To evaluate the effect of potential bias due to infection: association between adverse child outcomes and macrolides (versus penicillins) prescription during pregnancy, restricted to children of mother whose antibiotics were prescribed for respiratory tract infection (RTI).
3. To evaluate the potential effect of outcome misclassification for CP and malformations: define CP cases with diagnostic codes only, and identify malformation cases as only those with repeated (>=2) child diagnoses, or with diagnoses in both the maternal (18GW to 6 months postpartum) and child records (before age 3).
4. To evaluate the potential effect of live-birth bias: Evaluate the direction and quantity of the potential live-birth bias by simulating proportions of fetal deaths among women exposed to macrolides versus those exposed to penicillins.

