Prompt and adequate treatment for infection during pregnancy is vital given the well-established association between maternal infection during pregnancy and adverse birth outcomes, including miscarriage and stillbirth.(17) More evidence is needed on whether there is a causal association between maternal macrolide antibiotics treatment during pregnancy and adverse child outcomes.

2. Objectives

We will conduct a population-based cohort study to evaluate the association between the macrolide antibiotics prescription in pregnancy and adverse child outcomes (neurodevelopmental disorders and major malformation (overall and system-specific)) (**primary analysis**), and to examine this association by macrolides subtypes and length of prescriptions (**subgroup analysis**).

3. Data source

We will use the Clinical Practice Research Datalink (CPRD), a UK-representative database which captures prospective, anonymised data on prescriptions, diagnoses, and symptoms records in primary care.(18) A Mother-baby link was built within CPRD using family ID, practice ID, and date of birth/delivery, with details reported elsewhere.(19, 20) For each mother-baby pair, a delivery date was estimated (Appendix).

4. Methods

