4.4 Analyses

4.4.1 Statistical methods

Standardized differences will be used to assess covariate balance between the macrolides group and the penicillins group; meaningful imbalances are defined by an absolute standardized difference of more than 0.1.(30) For neurodevelopmental disorders, absolute rates of outcomes and unadjusted hazard ratios with 95% confidence intervals will be calculated. For malformations, absolute risks of outcomes and unadjusted risk ratios with 95% confidence intervals, will be calculated. Exposure propensity scores will be estimated as the predicted probability of receiving the macrolides prescription (vs. penicillins), conditional on the covariates described above, with the use of logistic-regression models. For each estimated propensity score, the population in the nonoverlapping areas of the propensity-score distributions will be trimmed, and 50 strata will be created on the basis of the distribution of the treated women.(31) Weights for the reference group will be calculated according to the distribution of the treated women among propensity-score strata. We then use the weight to estimate adjusted baseline characteristics, and adjusted hazard ratios (in Cox proportional hazard models with weight statement for neurodevelopmental disorders) or risk ratios (in log-binomial model with weight statement for malformations) as well as their 95% confidence intervals. To account for the clustering of siblings and multiple births within mother, robust standard errors will be estimated. The analyses will be conducted using RStudio version 3.5.1.. No adjustment will be made for multiple comparisons, and results for comparisons of exposure timing and subgroup analysis should be interpreted as exploratory.

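### Effects by macrolide subtype, prescription duration and trimester window are planned as stratum-specific ratios only, with no estimate of the difference between strata

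*Combined protocol and SAP*

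**What the plan says.** Section 2 sets a subgroup objective "to examine this association by macrolides subtypes and length of prescriptions". Section 4.4.2 carries this out with one analysis "by macrolide subtype (erythromycin, clarithromycin and azithromycin") and another described as "Association between adverse child outcomes and macrolide (versus penicillins) prescription during pregnancy, by duration of antibiotics prescription (<7days and >=7days"). The same section lists two timing analyses among the primary ones: "prescription during 1st trimester (from 5 to 13 GW") and "prescription during 2st to 3rd trimester (from 14 GW to delivery").

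The only estimation method is in section 4.4.1: weighted Cox models for neurodevelopmental outcomes and weighted log-binomial models for malformations, giving adjusted ratios "as well as their 95% confidence intervals. To account for the clustering of siblings and multiple births within mother, robust standard errors will be estimated". That section makes no multiplicity adjustment and adds that "results for comparisons of exposure timing and subgroup analysis should be interpreted as exploratory".

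The document contains no product term, between-subtype contrast, ratio of ratios or heterogeneity test. It does not describe the model structure for the subgroup analyses, nor say whether the penicillin group is also divided by duration.

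**The concern.** Results presented by subtype, length and timing will be read for differences: one macrolide but not another, long courses but not short, early exposure but not late. Section 4.4.1 itself speaks of comparisons of exposure timing. Two separate intervals against penicillin do not estimate such a difference. When strata differ in size, the smaller can miss significance while the larger reaches it, even though the true effect is the same in both.

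Timing matters particularly for malformations, because section 4.3.1 identifies 5 to 13 gestational weeks (GW) as the critical period for most of them. Whether the early-window effect exceeds the later one is informative, and the plan does not estimate it. What is at stake is the reading of the subgroup and timing results. The overall macrolide-versus-penicillin comparison is not affected.

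**Working it through.** **Inputs.** From section 4.5: about 10,000 macrolide and 100,000 penicillin pregnancies, RR 2, 5% significance, 80% power. From Table 2: baseline risks of 0.002 (cerebral palsy; genital, gastrointestinal and nervous system malformations), 0.003 (urinary), 0.006 (epilepsy, ADHD), 0.008 (ASD) and 0.02 (any major malformation). The documents give no stratum sizes, so 50/50 and 80/20 splits are assumed. RR 1.5 is an added assumption, used to show a smaller effect.

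**1. The plan's own rule.** With the arcsine effect size, two-sided 5%, at risk 0.002: h = 2·asin(√0.004) − 2·asin(√0.002) = 0.0371, and (1.960 + 0.842)²/h² ≈ 5,701. The macrolide group needed is 1/(1/5,701 − 1/100,000), about 6,047, which is below 10,000. At risk 0.001 the requirement is 12,893, which is above it. Table 2's inclusions and exclusions reproduce. The rule uses the whole macrolide group; no power is stated for any stratum.

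**2. Chance that exactly one of two strata is significant when the true RR is equal.** With n1 macrolide and n2 penicillin pregnancies in a stratum:

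SE(log RR) = √[1/(n1·p·RR) + 1/(n2·p)]; power = Φ(log RR/SE − 1.960); discordance = a(1 − b) + b(1 − a), where a and b are the two powers.

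Risk 0.002, RR 2, 50/50 (5,000 v 50,000 in each stratum): SE = √(1/20 + 1/100) = 0.245; z = 0.693/0.245 = 2.83; power 0.81. Discordance = 2 × 0.81 × 0.19 = 0.31.

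Risk 0.002, RR 2, 80/20:
- Larger stratum: SE = √(1/32 + 1/160) = 0.194, power 0.95.
- Smaller stratum: SE = √(1/8 + 1/40) = 0.387, power 0.43.
- Discordance = 0.95 × 0.57 + 0.43 × 0.05 = 0.56.

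| Baseline risk | True RR in both strata | 50/50 | 80/20 |
|---|---|---|---|
| 0.002 | 2 | 31% | 56% |
| 0.003 | 2 | 12% | 41% |
| 0.006 | 2 | about 0% | 13% |
| 0.008 | 2 | about 0% | 5% |
| 0.02 | 2 | about 0% | about 0% |
| 0.006 | 1.5 | 41% | 61% |
| 0.02 | 1.5 | 1% | 17% |

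Using the exact binomial variance, with (1 − p) terms, changes these by about one percentage point at most. A direct test of difference would have an error rate of about 5% under the same null.

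These figures treat the strata as independent, split the penicillin group in the same proportions, and allow nothing for weighting or clustering. They suit duration (if penicillin is also split) and trimester. They do not apply directly to subtypes, which would share one penicillin group.

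**3. Power of a direct test of difference.** Take RR 2 in one stratum (the smaller, if unequal) and 1 in the other, at risk 0.002.
- 50/50: variance = (1/20 + 1/100) + (1/10 + 1/100) = 0.17; z = 0.693/0.412 = 1.68; power 0.39.
- 80/20: variance = (1/8 + 1/40) + (1/16 + 1/160) = 0.219; z = 1.48; power 0.32.

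With an unsplit penicillin group, the 50/50 value is about 0.43. At risk 0.006, power is 0.83 (50/50) and 0.73 (80/20). At risk 0.02 it is about 1.00 for both.

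**The case against.** A reader might infer that the plan will decide subgroup questions by setting significant against non-significant results. The documents do not say so. They state no significance rule for subgroups or timing, they report estimates with intervals, and they call these results exploratory. The step 2 figures describe a misreading that the plan leaves open, not one that it prescribes.

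The objective is to examine the association by subtype and length, and stratum-specific estimates meet that wording. Trimester is not in that sentence; it enters through sections 4.4.1 and 4.4.2. That separate models will be fitted is a fair reading, but not an explicit statement. All of this stands. It does not supply an estimate of difference, and the exploratory label does not say which quantity would answer the question.

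The misreading risk is also uneven. At the plan's own RR of 2 it is concentrated in the rarest outcomes and nearly absent for any major malformation.

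A reader might also take the trimester ratio to be the plan's best internal check on confounding. The documents do not support that ranking. Section 4.4.2 already has a negative control 10-50 weeks before pregnancy and a restriction to respiratory tract infection. The ratio also depends on gestational dating, and the Appendix reports that 49.6% of babies were assigned 40 weeks by default.

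Finally, one product-term model with a single overall set of weights would be a poor remedy. It would not ensure covariate balance within duration or trimester strata, and nothing in it balances one subtype's users against another's.

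**Conclusion.** The gap is real and of moderate importance: three sets of stratum results are planned and no difference between strata is estimated. Informal contrasts would be least reliable for outcomes with baseline risk near 0.002, where equal true effects at RR 2 give discordant significance in 31% to 56% of studies. They would also be unreliable at 0.006 if the true RR is nearer 1.5 (41% to 61%). They would be much safer for any major malformation: about 0% at RR 2, and 1% to 17% at RR 1.5. The sizes rest on the assumed splits and on independent strata; none is offered for subtype. The overall comparison and Table 2 are untouched.

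**What to change.** Add a paragraph to section 4.4.2:

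- **Duration and trimester.** Keep the stratum-specific estimates, with the propensity score and weights re-estimated within each stratum, and state whether penicillin users are also divided by duration. Add the ratio of hazard or risk ratios between strata, with a 95% CI clustered on mother (robust or cluster bootstrap).
- **Subtype.** Weight each subtype comparison with penicillin separately. Report between-subtype ratios and one 2-df heterogeneity test that allows for the shared penicillin group. Note that residual case-mix differences between subtypes may remain.
- **Claims.** State that a difference by subtype, length or timing will be claimed only on these ratios, and that a null test is not evidence of equality.
- **Malformations.** Report the ratio of the 5-13 GW effect to the effect from 14 GW to delivery as a supplementary check alongside the negative control, with the caveat that gestational age was imputed as 40 weeks for 49.6% of babies.

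No new data are needed. The cost is extra analysis work (separate scores, weights and a joint variance, which is more than adding a product term), further unadjusted exploratory results, and wide intervals: power is about 0.3 to 0.4 for the risk-0.002 outcomes at RR 2 versus 1.

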4.3.3 Covariates

We will control the covariates which are potential risk factors for adverse child outcomes. These include: 1) maternal characteristics at baseline (i.e. age at child birth, problematic alcohol use, illicit drug use, recent tobacco use, and obesity); 2) pregnancy related variables (i.e. birth year, parity, multiple birth, hypertension, diabetes, epilepsy, depression, anxiety, maternal chronic medical conditions during pregnancy, potentially fetal-damaging maternal infection during pregnancy, and baby gender) (details given below). Gestational age at delivery and Apgar score after birth are considered mediators on the pathway for the association between prenatal antibiotics exposure and adverse child outcomes and therefore not adjusted.

1. *Maternal variables*

1) **Maternal age (at birth)**

By 5 year categories.

2) **Maternal life style:**

a. Problematic alcohol use:

Most recent record between 10 years prior to and during pregnancy:

- a Read code indicating alcohol misuse; or
- a prescription for disulfiram or acamprosate; or
- self-reported average weekly alcohol intakes of between 14-500 units of alcohol a week.

b. Illicit drug use:

Most recent record between 10 years prior to and during pregnancy:

- a read code for drug use, addiction, and overdose; or
- a prescription for methadone treatment

c. Recent smoking/tobacco use:

Most recent record between 3 years prior to and during pregnancy:

- self-reported daily cigarette consumption of 1-100 cigarettes per day unless there was evidence of smoking cessation; or
- a read code indicating tobacco consumption; or
- a prescription to assist smoking cessation

d. Obesity

Most recent record from 3 years prior to the end of 1st trimester:

A read code for obesity (or a BMI of ≥ 30 kg/m² - either directly entered or calculated from the most recent height measurement and median pre-pregnancy weight after outliers, i.e. height outside the range 1-2m and weight outside the range 35-300kg, were removed).

2. *Pregnancy related variables*

3) **Baby birth year**

Grouped into categories of 5 calendar years.

4) **Parity**

Categorised as "0", and " ≥ 1 ".

5) **Multiple births**

Categorize the baby as "singleton", or "(one of the) twin, triplets, or quadruplets".

6) **Hypertension**

Measurement from 50 weeks prior to delivery:

- systolic and diastolic blood pressure was above 140mmHg and 90mmHg, respectively, or

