- a Read codes for hypertension and associated diagnoses (including pre-eclampsia, eclampsia and HELLP syndrome), or
- a prescription for hypertension drugs from sections 2.2 and 2.5 of the BNF. This variable identified mothers with both treated and untreated hypertension in pregnancy.

7) **Diabetes**

Measurement from 50 weeks prior to delivery:

- a Read code for type I, type II, or gestational diabetes;
- two or more prescriptions for anti-diabetic medication; or
- laboratory tests indicative of diabetes (defined as ≥ 2 abnormal glucose tests, fasting glucose >7.0 millimoles per litre [mmol/L] or >126 milligrams per decilitre

[mg/dL], plasma glucose after glucose tolerance test >11.1 mmol/L or 200mg/dL, glycated haemoglobin \geq 6.5%, or with diabetes annual review).

8) Epilepsy

Measurement from 50 weeks prior to delivery: 2 prescriptions of antiepileptic drugs (AEDs) within 4 months or \geq 1 diagnosis

9) Depression

Measurement from 50 weeks prior to delivery: \geq 2 occurrences of diagnostic code, treatment code or symptom

10) Anxiety

Measurement from 50 weeks prior to delivery: \geq 2 occurrences of diagnostic code, treatment code or symptom

11) Treatment of chronic medical conditions during pregnancy

Measurement during pregnancy: two or more prescriptions (on separate days during pregnancy and not more than four months apart) for drugs from the same BNF section or paragraph. Drugs used to treat common conditions in pregnancy such as reflux (BNF section 1.2), nausea and vomiting (BNF section 4.6), and constipation (BNF section 1.3) were not included.

12) Potentially fetal-damaging infections during pregnancy.

Mothers are classified as having a potentially fetal-damaging infection in pregnancy if they had recorded at any time during their pregnancy, a Read code for a diagnosis or a laboratory test confirming any of the following infection: genitourinary infection, "TORCH" (Toxoplasmosis, Other agents such as HIV, Rubella, Cytomegalovirus and Herpes simplex) and sexually transmitted infections (STIs). "TORCH" and STIs have long been known as important risk factors to adverse pregnancy outcomes and teratogenic pathogens. (22, 23) Intrauterine infection has been recognised as an important mechanism of disease in preterm labor. (24) Hyelonephritis and bacteriuria have also been linked with preterm labor and low birthweight. (25)

3. Neonatal variables

13) Baby gender

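### The primary propensity score omits the indication and gestational week of the index prescription, leaving the primary estimates open to residual confounding of unknown size and direction

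*Combined protocol and SAP*

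**What the plan says.** Section 4.4.1 estimates the propensity score "conditional on the covariates described above, with the use of logistic-regression models", so its content is the list in section 4.3.3. That section states its aim as "We will control the covariates which are potential risk factors for adverse child outcomes". The list has two parts:

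- A baseline part: "maternal characteristics at baseline (i.e. age at child birth, problematic alcohol use, illicit drug use, recent tobacco use, and obesity".
- A pregnancy part, whose only infection entry is "potentially fetal-damaging maternal infection during pregnancy, and baby gender". Item 12, headed "Potentially fetal-damaging infections during pregnancy", defines this entry as "a Read code for a diagnosis or a laboratory test confirming any of the following infection: genitourinary infection", TORCH infections and sexually transmitted infections, recorded at any point in the pregnancy.

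The paragraph before section 2 describes maternal infection as an established correlate of adverse birth outcomes. Section 4.4.2 names possible bias due to infection and assigns it to sensitivity analysis 2, "restricted to children of mother whose antibiotics were prescribed for respiratory tract infection (RTI".

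On timing, section 4.3.1 sets the index date at the first prescription and describes weeks 5 to 13 as the critical period for most major malformations. Section 4.4.2 lists three primary analyses: the whole window, first trimester, and second to third trimester. Section 4.4.1 asks for comparisons of exposure timing to be read as exploratory.

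**The concern.** The comparison is between two antibiotics, so the main threat is that they are chosen for different infections, or at different stages of pregnancy, and that those differences carry their own risk. The score can balance only what is in it. A woman's respiratory infection is not in it. A genitourinary infection is, but the record need not relate to the index prescription and may come after it.

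The other planned steps do not fill the gap in the primary estimate:

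- Balance is assessed on the covariates, so an imbalance in an unlisted indication would go unseen.
- The negative control cohort uses prescriptions before conception and addresses maternal baseline characteristics, not infection during pregnancy.
- The respiratory restriction gives a second, smaller estimate for one indication and leaves the primary ratios as they were. It also uses the whole of pregnancy, so it does not hold timing fixed.

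At stake is whether a modest primary hazard or risk ratio can be attributed to the drug rather than to the reason for, or timing of, its prescription.

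**Working it through.** **Inputs from section 4.5.** About 10,000 macrolide and 100,000 penicillin pregnancies; baseline risks in Table 2, including 0.002 for cerebral palsy and 0.02 for any major malformation; 80% power for a risk ratio of 2 at the 5% level (two-sided assumed).

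**1. The plan's own figures.** No stated figure bears directly on confounding, but the Table 2 decisions can be checked. With h = |2·arcsin√(2p) − 2·arcsin√p|, solve n1·n2/(n1+n2) = ((1.960 + 0.842)/h)² for n1 with n2 = 100,000. At p = 0.002, h = 0.0371 and n1 = 6,047, below 10,000 (included). At p = 0.001, n1 = 12,893 (excluded). All the decisions in the table reproduce. This confirms the group sizes used below; it neither supports nor refutes the concern.

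**2. Bias from an omitted binary indication (shares and risks assumed).** Let pM and pP be its share in the macrolide and penicillin groups, and r the risk ratio it carries. Under a true null the observed ratio is

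B = [1 + pM(r − 1)] / [1 + pP(r − 1)].

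| pM / pP | r = 1.2 | r = 1.5 | r = 2 |
|---|---|---|---|
| 0.5 / 0.5 | 1.000 | 1.000 | 1.000 |
| 0.6 / 0.5 | 1.018 | 1.040 | 1.067 |
| 0.7 / 0.5 | 1.036 | 1.080 | 1.133 |
| 0.7 / 0.4 | 1.056 | 1.125 | 1.214 |
| 0.8 / 0.4 | 1.074 | 1.167 | 1.286 |
| 0.4 / 0.6 | 0.964 | 0.923 | 0.875 |

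The formula treats the indication as wholly unadjusted. To the extent that item 12 captures it, the bias is smaller.

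**3. Size against sampling error.** Take pM = 0.6, pP = 0.4, r = 1.5: B = 1.30/1.20 = 1.083, log B = 0.080. The crude standard error of the log ratio, ignoring weighting and clustering, is √(1/events in macrolide group + 1/events in penicillin group) under the null.

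- Any major malformation: √(1/200 + 1/2,000) = 0.074; bias 0.080/0.074 = 1.08 SE.
- ASD: √(1/80 + 1/800) = 0.117; 0.68 SE.
- Epilepsy: √(1/60 + 1/600) = 0.135; 0.59 SE.
- Cerebral palsy: √(1/20 + 1/200) = 0.235; 0.34 SE.

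For any malformation, the chance of a nominally significant result under a true null would be P(Z > 1.96 − 1.08) + P(Z < −1.96 − 1.08) = 0.189 + 0.001, about 19%. For cerebral palsy it would be P(Z > 1.62) + P(Z < −2.30) = 0.053 + 0.011, about 6%.

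**4. What the respiratory restriction can carry.** If the same share s of each group had a respiratory indication (assumed), power for a risk ratio of 2 at baseline risk 0.002 is 49% at s = 0.3, 71% at s = 0.5 and 84% at s = 0.7, against 94% in the full cohort. The plan's 80% criterion needs s of about 0.63. At baseline risk 0.006, power is 92% or more for s of at least 0.3.

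**The case against.** The case for leaving the plan alone has weight.

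- **Infection is partly handled.** The comparator is itself an antibiotic, so both groups were treated, and item 12 puts into the score the infections that the plan regards as fetal-damaging. A reader might infer that the score ignores infection; it does not. Nor do the documents say that respiratory infection raises the risk of these particular outcomes. This narrows the gap to indications outside item 12 and to the missing link between infection record and prescription.
- **Timing is partly handled.** Two of the three primary analyses split exposure at 14 weeks. A reader might infer that timing is a bias the plan admits to; the plan names only infection. What remains is the pooled analysis and variation within two broad windows.
- **Gestational age at delivery is left unadjusted on purpose, as a mediator.** That is a different variable from the week of the index prescription and does not justify omitting the latter.
- **Restriction holds indication fixed more directly than adjustment.** True, and a reason to keep it. It covers one indication, may be underpowered for the rarest outcomes, and does not alter the primary estimate.
- **The remedy is imperfect.** Many prescriptions may have no recorded indication. By the Appendix, 49.6% of gestations are imputed at 40 weeks, and some others come from delivery markers, such as premature labour set at 36 weeks. Both limits are real, although the same dating already defines the exposure windows.

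**Conclusion.** The point stands as a gap in the primary adjustment set, not as a demonstrated bias. Index indication and index gestational week are absent from the score. The infection bias that the plan names is addressed beyond item 12 only in a sensitivity analysis.

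Two stronger conclusions are tempting. One is that the primary ratios are confounded; the other is that the bias would make macrolides look worse. The documents support neither, because they give no mix of indications or prescription weeks by drug. Confounding requires one of these to differ between drugs and to predict outcome within score strata. Under the assumed shares and risks the factor runs from about 0.88 to 1.29, and is 1.00 if the shares are equal. Nor does an 8% bias matter equally everywhere: it reaches about one standard error only for any major malformation, the most common outcome in Table 2, and is about 0.34 for cerebral palsy. It is also small beside the risk ratio of 2 used for power.

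The change is still worth making: modest ratios for the commoner outcomes are where such a bias could mislead.

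**What to change.** In sections 4.3.3 and 4.4.1, add two terms to the logistic propensity model for all primary analyses:

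1. Recorded indication of the index prescription, at minimum three categories: respiratory; genitourinary or sexually transmitted; other or none recorded. State the rule that links a diagnosis to a prescription, and apply the same rule in sensitivity analysis 2.
2. Gestational week at the index prescription, as a continuous or spline term.

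Report standardized differences for both, before and after weighting, against the plan's 0.1 threshold. Keep the respiratory restriction as the sensitivity analysis. If either term is left out, the plan should justify the omission.

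Costs: sensitivity analysis 2 already presupposes a respiratory indication, and the index date and gestational dating already exist. However, the plan states no linkage rule and no multi-category indication variable, so a rule and possibly a further code list must be written. The no-recorded-indication group may be large and leave some confounding inside it. Trimming of non-overlapping scores may remove slightly more women. Index week will carry the dating error described in the Appendix.
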